1. ABSTRACT

Background: The effectiveness of colonoscopy in reducing colorectal cancer mortality relies on the detection and removal of neoplastic polyps. Because the risk of prevalent cancer and of transition to cancer increases with polyp size, effective and safe resection of large polyps is particularly important. Large polyps $\geq 20\text{mm}$ are removed by so-called endoscopic mucosal resection (EMR) using electrocautery snares. Resection of these large polyps is associated with a risk of severe complications that may require hospitalization and additional interventions. The most common risk is delayed bleeding which is observed in approximately 2-9% of patients. A recent retrospective study suggests that closure of the large mucosal defect after resection may decrease the risk of delayed bleeding. However, significant uncertainty remains about the polypectomy techniques to optimizing resection and minimizing risk. Important aspects that may affect risk include clipping of the mucosal defect and electrocautery setting.

Aims/Hypothesis: Our primary aim is to examine whether clip closure of the mucosal defect after endoscopic mucosal resection (EMR) of large polyps ($\geq 20\text{mm}$) will reduce the risk of delayed bleeding in a prospective randomized trial. In secondary analysis we will explore, whether electrocautery settings affect the risk of complications. We hypothesize that clip closure will reduce the risk of delayed bleeding.

Methods: The study will include patients with a polyp $\geq 20\text{ mm}$ in size. Experienced endoscopists will follow a standardized resection protocol. Patients will be randomized in a 2×2 factorial design to one of two electrocautery settings (Endocut versus low power coagulation; secondary comparison) and to either undergo or not undergo closing of the mucosal resection defect after resection. For the primary comparison (clip vs. no clip) the primary outcome will be incidence of delayed bleeding complications within 30 days following the procedure. We further plan to identify factors that may be associated with delayed bleeding. We are also interested in understanding recurrence of neoplastic polyps at first and second follow-up colonoscopy, defined as the presence of biopsy proven neoplastic tissue.

Anticipated Results: The results of the study will help to determine whether clip closure of the mucosal defect after resection of large polyps is associated with a decreased delayed bleeding risk. The results will further help to understand whether there is a preferred electrocautery setting with a lower complication risk. The findings may therefore help to identify a safe resection practice and contribute to the development of resection standards for polypectomy.

2. SPECIFIC AIMS

Aim 1. The primary aim of the study is to compare the rate of delayed bleeding complications in patients undergoing endoscopic resection of large polyps between:

- A) Closing the mucosal defect after resection (Clip group) and
- B) Not closing the mucosal defect after resection (No clip group).

Aim 2. The secondary aim of the study is to compare the rate of overall complications in patients undergoing endoscopic resection of large polyps between two cautery settings:

- A) Low power coagulation and
- B) Endocut.

Hypothesis: Specific endoscopic techniques are associated with a lower complication rate of endoscopic mucosal resection of large colorectal polyps.

Additional secondary aims: The study further examines the rate of complete polyp resection, polyp recurrence, and factors that are associated with complete resection and recurrence during 5 years of follow-up.

3. RESEARCH PLAN

3.1. Background and Significance

Colorectal cancer is the second most common cause of cancer death in the United States¹. The effectiveness of colonoscopy in reducing the risk of dying from colorectal cancer relies on the detection and safe resection of neoplastic polyps to prevent incident cancers. Most polyps are small and can be easily removed using snare with or without electrocautery. Because the risk of prevalent cancer or transition to cancer increases with polyp size, effective and safe resection of large polyps is particularly important.

Endoscopic mucosal resection (EMR) is evolving as the primary endoscopic technique to remove large non-pedunculated polyps. These flat or sessile polyps are defined as lateral spreading tumors with a low vertical axis that extend laterally along the luminal wall. Several mostly retrospective studies from Europe, the U.S. and Japan, have demonstrated a high “cure” rate, with results lending credence to the shift from surgical resection to endoscopic management of these lesions. Of concern, however, is 1) a fairly high overall complication rate of 8-26% in prospective studies²⁻⁶, and 2) the persistence of residual neoplasia on follow-up endoscopy ranging from 16% to 46%^{2, 5, 7}.

3.1.1. Complications of endoscopic mucosal resection of large polyps

Severe complications that are associated with a standard screening colonoscopy, which may include resection of predominantly smaller polyps, are uncommon. Significant bleeding occurs in 0.2 to 0.5% of patients (defined as a 2gm drop in Hemoglobin), perforation of the colon in 0.05-0.10%, and post polypectomy syndrome in <0.5%^{8, 9}.

The risk of severe complications increases with polyp size. The incidences of complications associated with resection of large polyps are summarized in table 1. The most common complication is bleeding reported in 2 to 24% of polyp resections. Perforation occurred in approximately 1% of resections and postpolypectomy syndrome in 1-4% of patients.

Postpolypectomy syndrome is caused by focal inflammation as a result of deep cautery injury to the serosal surface when resecting a polyp. Patients typically present with abdominal pain, fever, and leukocytosis.

In addition to size, other factors that may affect complications. These include type of resection (piecemeal versus en-bloc), polyp location (right colon with a thinner wall than the left colon), age and comorbidities, especially those that affect clotting abilities (e.g. renal insufficiency, liver disease, use of anticoagulation). Studies that have examined variables, which may directly decrease the risk of complications associated with large polyp resection, are limited.

Table 1. Studies that examined complications related to EMR of large colon polyps.

Study	Design	Patients n	Size	Electro-cautery	Compli-cations, overall	Bleed-ing	Perfo-ration	PPS
Walsh 1992 ¹⁰	Retrospective	108	≥10mm	Unclear	10.2%	9.3%	0.9%	-
Brooker 2002 ²	Prospective	34	≥15mm	Low power coag	26.5%	23.5%	0	-
Ahmad 2002 ¹¹	Retrospective	29	8-30mm	Unclear	24.1%	24.1%	0	0
Conio 2004 ³	Prospective	136	≥ 20mm	Blended	14.7%	-	0	3.7%
Kaltenbach 2007 ¹²	Retrospective	125	≥ 10mm	Blended	1.8%	1.8%	0	0
Arebi 2007 ⁷	Retrospective	161	≥ 20mm	Blended	8.2%	5.7%	0	-
Luigiano 2009 ¹³	Retrospective	148	≥ 20mm	Unclear	12.2%	10.1%	0.7%	1.4%
Swan 2009 ⁶	Prospective	174	≥ 10mm	Blended	16.2%	9.8%	0	-
Ferrara 2010 ⁴	Prospective	152	≥15mm	Blended	18.4	14.5%	1.3%	2.6%
Moss 2011 ⁵	Prospective	464	≥ 20mm	Blended	7.7%	2.9%	1.3%	1.5%
Gimeno-Garcia 2012 ¹⁴	Retrospective	1894	≥ 10mm	Unclear	Na	9.1%	Na	Na
Buchner 2012 ¹⁵	Retrospective	249	8-100mm	Low power coag	11.6%	10.0%	0.4%	1.2%
Qumseya & Wallace 2012 ¹⁶	Retrospective	525	≥ 20mm	Low power coag	Na	7.0%	Na	Na
Liaquat & Rex 2013 ¹⁷	Retrospective	420	≥ 20mm	Low power coag	Clip: 5.8% No clip: 12%	3.1% 8.8%	0.5%	1.2%

PPS = postpolypectomy syndrome (synonymous for transmural burn syndrome)

3.1.2. Limitations of prior studies

Prior studies (table 1)

- Studies often included polyps of <20mm. Because of the association between size and complications, results from these studies do not reflect complications with resection of ≥20mm polyps.
- Most studies were retrospective. Complications following within a 30-day window may go unnoticed (selection bias). There are few larger studies that evaluated complications prospectively. The risk of overall complications varied between 8% and 18%, with a bleeding risk between 3% and 14%.

Proposed study

The study will only include patients with non-pedunculated ≥20mm polyps.

The design will be a prospective RCT.

- The follow-up interval was not always clear, which may also lead to underreporting of delayed complications.
- The definition of what was considered a complication was not always provided.
- The denominator of how complications were measured was not always clear. The incidence could be related to number of polyps or number of patients (a patient could have more than one polyp).

Complications will be assessed within 30 days following the procedure.

Complications will be defined as clinical events following polyp resection, which require a visit to the ED, admission, or additional tests or procedures (see outcome measures).

We will calculate the incidence of complications per polyp and per patient.

3.1.3. Electrocautery and complication risk

Electrocautery snare resection represents the standard approach to resecting larger polyps. The principle of electrocautery snare resection relies on the application of an electrical current to the snare while closing the snare around the base of the polyp. Electrical energy is converted to heat energy by changing from a low frequency current (60Hz) to a high frequency current (>300,000Hz).

Two types of currents can generally be distinguished, cutting current and coagulation current. Cutting current delivers a high frequency (density) and low voltage current, which results in high-energy intensity and allows swift “cuts” through tissue without deep thermal tissue injury. The flip side is that it does not provide sufficient cautery time to seal cut blood vessels and bleeding is therefore a concern.

In contrast, coagulation current delivers a lower frequency (density) current. This current allows “sealing” of cut vessels and may prevent bleeding, but may cause deeper tissue injury and increase the risk for postpolypectomy syndrome and perforation. For polyp resection the so-called *low power coagulation* is used to resect polyps.

Two minimize risk, cautery units provide a setting of cutting current alternating with coagulation current, also called blended current. Realizing that heat production is dependent on tissue resistance, some cautery units provide a special type of blended cautery setting (also called “Endocut” when used with the ERBE cautery unit, which will be used in the study). Endocut is a microprocessor-controlled current alternating between coagulation and cutting adjusted for tissue resistance.

The rationale for assessing electrocautery current is very strong. It is a fundamental aspect of polypectomy and not a single randomized trial has been done to address its effect on complications. Endoscopists do polypectomy the way they were trained to do it. It is not an issue that is settled. In the 2004 a survey by Singh et al found that 46% of US endoscopists used blended current and 46% use low power coagulation¹⁸. Two retrospective studies found that low power coagulation causes delayed bleeding and blended current causes immediate bleeding^{19, 20}. Thus the type of current used for polyp resection remains an important clinical question.

3.1.4. Clipping and complication risk

It is apparent that resection of a large polyp leaves behind a large mucosal defect. The mucosal ulcer that forms after polyp resection can take several weeks to heal. Bleeding complication typically occur within 7 to 10 days, requiring often admission, a repeat

colonoscopy to stop bleeding, and possible blood transfusions. To reduce the risk of bleeding it has been proposed to close the mucosal defect after polyp resection.

To date, no randomized trial has examined whether clip application affects complications after large polyp resection. One recent study did not show a benefit²¹. Bleeding occurred in 2% in either group. However, the study included patients with smaller polyps (mean size 8mm) with a low expected bleeding risk. A recent retrospective study by Liaquat et al. showed that clip closure was associated with a significantly reduced risk of delayed bleeding (2% vs. 10%), and a reduced risk of overall complications (4% vs. 12%), when compared to historical controls²². Main limitations of the study include unmeasured factors that may have affected the outcome and performance of all resections by one expert colonoscopist. However, a third very recent retrospective study by Qumseya et al. reviewed their experience with 525 large colon polyp resection and did not find that clip closure was associated with delayed bleeding complications¹⁶.

In clinical practice use of clips after polyp resection is largely dependent on endoscopist preference and availability. In preparation for this study informal evaluation of polyp resection practice showed that some endoscopists use clips, and others do not. The unclear benefit with using clips, the required technical skills to achieve clip closure of the mucosal defect, and the additional cost may prevent some from using clips routinely.

Whether clip application prevents bleeding and other complications following resection of large polyps and may reduce overall cost of care remains an important clinical question: there is no established superior method, the issue arises daily, the potential impact on clinical practice from a definitive trial would be significant, both to establish an optimal approach and in terms of patient benefits.

3.2. Research Design and Methods

3.2.1. Design and patients

General study design: The study will be designed as a multicenter multi-endoscopist randomized trial.

A schematic diagram of the study design, procedures and stages is detailed in Figure 1, Appendix 3.

Study participants: Potential study participants will include patients with a colonic non-pedunculated polyp $\geq 20\text{mm}$ in size considered for endoscopic resection (see inclusion and exclusion criteria).

Anticipated number of research subjects (see also sample size calculation):

- Estimated number of participants for duration of entire study: Female: 470, Male: 550 (several sites are VA Medical Centers)
- Estimated total number at each site: ≥ 20

3.2.2. Inclusion and Exclusion criteria

Inclusion criteria:

- Any patient ≥ 18 and ≤ 89 who presents for a colonoscopy and who does not have criteria for exclusion
- Patients with a $\geq 20\text{mm}$ colon non-pedunculated polyp

Exclusion criteria:

- Patients with known (biopsy proven) invasive carcinoma in a potential study polyp
- Pedunculated polyps (as defined by Paris Classification type I_p or I_{sp})
- Patients with ulcerated depressed lesions (as defined by Paris Classification type III)
- Patients with inflammatory bowel disease
- Patients who are receiving an emergency colonoscopy
- Poor general health (ASA class>3)
- Patients with coagulopathy with an elevated INR ≥ 1.5 , or platelets < 50
- Poor bowel preparation
- Pregnancy

We will document patients who were referred for a resection of a large polyp, but were not consented. For these patients (not study subjects) we will record the reason for not consenting (e.g. did not elect to participate, patient met exclusion criteria, etc.), the patient's age and gender.

Similarly, we will collect information on reasons for exclusion of polyps (including size, morphology, and location).

3.2.3. Study screening procedures

To determine patient eligibility:

- Review of the patient's personal medical history
- Review of medical records to verify patient inclusion and exclusion criteria (age, comorbid conditions, anticoagulation).

To determine polyp eligibility:

- Examining eligibility of a potential study polyp during the colonoscopy with respect to polyp inclusion and exclusion criteria (size, morphology).

Potential study participants include patients with a ≥ 20 mm non-pedunculated colorectal polyp (= study polyp).

Identification of study participants:

- Patients with a known ≥ 20 mm polyp detected at a prior colonoscopy and referred for resection of this polyp.
Patient characteristics (age), comorbidities (see exclusion criteria), and medications (exclusion of coagulopathy) will be reviewed prior to the procedure. The patient will be informed about potential study participation. If the patient agrees to participate and after informed consent is provided, the colonoscopy will be performed. Whether a polyp will meet inclusion criteria (size and morphology) will be determined during the colonoscopy. If the patient does not have a polyp that meets the inclusion criteria, the patient will not be included and considered a screen failure.

An alternative subject identification may be applied at some centers with fewer referrals for polyp resection. Any patient who is scheduled for an elective colonoscopy will be provided with an information sheet that allows him/her to opt out to be considered for study enrollment. If the patient does not opt out and if an eligible study polyp is detected during the colonoscopy, the patient may be randomized to one of the four protocol arms (only if patient and polyp inclusion/exclusion criteria are met). The Polyp resection will be performed as determined by randomization. Following the procedure the patient will be informed about the

randomized approach to polyp resection and informed about potential participation in the study. Only after the patient provides informed consent, he/she will be included in the study (see Alternative Consent Process).

3.2.4. Patients on anticoagulation

Patients on anticoagulation medications will be managed according to the ASGE guideline²³. According to the guideline, polypectomy is considered a high-risk procedure. All study procedures are elective procedures. In accordance with the guideline, the type of anticoagulation and the patient risk for a thromboembolic event will determine the decision on managing periprocedural anticoagulation.

3.2.5. Allocation to treatment (Randomization process)

Randomized will occur at the time of colonoscopy when a polyp has been identified as a study polyp using computer generated randomization. Patients will be randomized following a 2 x 2 factorial design to: (i) Endocut vs. low power coagulation after inspection of the polyp and decision to resect the polyp, and (i) clipping vs. no clipping of the mucosal defect after resection.

Patients will hence be randomized to one of four groups:

- A) Endocut and clipping,
- B) Endocut and no clipping,
- C) Low power coagulation and clipping, and
- D) Low power coagulation and no clipping.

Should a patient have more than one study polyp, all polyps will be resected in the same way (per patient randomization). The primary comparison will be between clip and no clip application. The comparison between cautery currents is secondary and exploratory.

Breaking the blind: The study is not blinded.

Treatment adherence/study compliance: The primary intervention (one-time clip placement) does not require adherence to the intervention. Participants will therefore not be excluded because of non-compliance.

The major outcome of interest will be assessed after 30 days following the intervention by a phone call. We expect that such short interval will allow an almost complete follow-up.

Secondary outcomes of interests include polyp recurrence during longer-term follow-up. We will collect data on all follow-up procedures that are performed as per standard of care (not as a study intervention).

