Following resection, the endoscopist will confirm that the polyp appears to be completely resected macroscopically by detailed examination of the resection margin. Visible remaining polyp tissue should be resected or ablated (typically using argon plasma coagulation [APC]). Once resection is considered complete the mucosal defect will be either closed or not closed with clips, as determined per randomization protocol. After resection, the site will

be marked with spot injection to identify the polyp site at a future endoscopy (standard of care).

In some circumstances the endoscopist may consider it as clinically appropriate to place a clip, even if the patient was randomized to the non-clipping group. Such situations may include, but are not limited to placing a clip to control bleeding during the polyp resection. In these situations the endoscopist will be asked to document the reason for clip placement.

Following the procedure patients will be observed in recovery as per standard of care at each institution.

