3.2.10.4. Sample Size Determination

Our sample size calculation is based on the primary aim. We hypothesize that polyp resection with clip closure of the mucosal defect will reduce the incidence of delayed bleeding complications. Prior studies have reported an overall bleeding incidence between 2 and 24% (table 1). We consider an absolute difference of 5% in delayed bleeding incidence (e.g. 8% and 3%) as clinically important. Assuming a two-sided alpha of 0.05 and a power of 80%, the study will need to include a total of 730 subjects (365 subjects into each group) to show such difference as significant. We assume that for approximately 20% of patients clip

closure will not be considered possible. Therefore approximately 920 patients will need to be included. However, approximately 10% of potential study polyps of referred patients will not meet inclusion criteria (screen failures). We estimate therefore that we need to enroll (=consent) a total of 1,020 patients for 920 patients to undergo the study intervention.

Because the primary outcome measure (delayed bleeding) will be assessed after 30 days of the colonoscopy we do not expect any dropouts.

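### When the clip arm is allocated is ambiguous, and no text withholds it until resection is complete or has closability recorded in both arms first

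*Combined protocol and SAP*

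**What the plan says.** Section 3.2.5 fixes one moment for randomisation: "Randomized will occur at the time of colonoscopy when a polyp has been identified as a study polyp using computer generated randomization". The next sentence gives the two factors of the 2×2 design different time markers: "Endocut vs. low power coagulation after inspection of the polyp and decision to resect the polyp", and then "clipping vs. no clipping of the mucosal defect after resection". The section continues "Patients will hence be randomized to one of four groups" and lists the four cautery-by-clip combinations. It also says that the study is not blinded and that allocation is per patient, so all study polyps in one patient are treated alike.

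Section 3.2.3, on the alternative identification route, says "if an eligible study polyp is detected during the colonoscopy, the patient may be randomized to one of the four protocol arms"; resection then follows the randomised assignment.

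Section 3.2.6 times the clip step itself: "Once resection is considered complete the mucosal defect will be either closed or not closed with clips, as determined per randomization protocol". It does not say when the endoscopist learns the assignment.

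On closability, a sentence in Section 3.2.10.4 begins "We assume that for approximately 20% of patients clip" and goes on to say that closure will not be considered possible; the sample size is raised for this. Closability is not an eligibility criterion (Sections 3.2.2 and 3.2.3). Section 3.2.9.2 records the degree of closure achieved (complete, partial or none) as an explorative item. The primary test is by intention to treat (Section 3.2.10.1).

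**The concern.** If all four arms are assigned when the polyp is identified, the endoscopist can know throughout the resection whether the defect is to be closed. Much of the technique is left to the endoscopist: the lifting agent, whether to inject at all, and the snare (Section 3.2.6). Someone who expects the defect to stay open may work differently from someone who expects to close it. Such a difference arises after randomisation and before the intervention under test. An intention-to-treat analysis keeps it in the comparison and cannot separate it from the effect of clipping.

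The second strand is closability. The 730 patients before inflation correspond to those in whom closure is possible. Degree of closure achieved cannot show which defects in the no-clip arm could have been closed. A later analysis of feasible patients would then have no like-for-like control group unless closability is assessed in both arms without knowledge of the arm.

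The primary and secondary endpoints are meant to support clip labelling (Section 3.2.10.1), so the allocation procedure should be clear.

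**Working it through.** **1. The timing texts side by side.**
- Section 3.2.5, timing sentence: randomisation at polyp identification. Alone, this puts both factors before resection.
- Section 3.2.3, alternative route: one of four arms once an eligible polyp is detected. A four-arm assignment includes the clip arm.
- Section 3.2.5, factor sentence: cautery after the decision to resect, clipping after resection. This can mean a second draw after resection, or only that clips are placed then.
- Section 3.2.5, four-group list: fits either reading, since two successive draws also give four groups.
- Section 3.2.6: times clip placement, not release of the assignment.

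Both readings are open and nothing available excludes early release. Even with a late draw, per-patient allocation could reveal the arm before later polyps are resected in patients with several study polyps (about 5%, Section 3.2.10.1).

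**2. The plan's sample size.** Inputs from Section 3.2.10.4: 8% versus 3%, two-sided alpha 0.05, power 80%.
- n = [1.96·√(2·0.055·0.945) + 0.842·√(0.08·0.92 + 0.03·0.97)]² / 0.05², giving 326 per arm.
- The continuity correction gives 365 per arm, 730 in total, as stated.
- 730/0.80 = 913 (stated 920). 920/0.90 = 1,023 (stated 1,020). Both agree to rounding.

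**3. What an arm-dependent shift could do (illustration).** Inputs: 920/2 = 460 per arm; final alpha 0.044 (Section 3.2.10.3), so z = 2.014. The clip-arm rate is 3%, or 4% if the 20% not closable bleed at 8% (assumption): 0.8×3% + 0.2×8% = 4%. The shift in no-clip bleeding is an assumption with no source in the documents.

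Power ≈ Φ{[d − z·√(2p̄(1−p̄)/n)] / √([p₁(1−p₁)+p₂(1−p₂)]/n)}, where d = p₁ − p₂ and p̄ is their mean.
- 8% versus 4%: (0.04 − 2.014×0.01566)/0.01560 = 0.54, power 71%.
- 7% versus 4%: (0.03 − 2.014×0.01503)/0.01500 = −0.02, power 49%.

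Exact binomial calculation of the same pooled z-test:

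| No-clip rate | Clip arm 4% | Clip arm 3% |
|---|---|---|
| 8% (no shift) | 71.6% | 91.9% |
| 7% | 49.7% | 79.3% |
| 6.5% | 37.8% | 69.6% |

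A one-point fall costs 71.6 − 49.7 = 21.9 or 91.9 − 79.3 = 12.6 points of power. The gap between the two columns is dilution by non-closable defects, which is a separate matter. A shift in the other direction would exaggerate the apparent benefit of clipping.

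**4. Why closability must be recorded in both arms.** Suppose clipping has no effect, overall bleeding is 8%, and non-closable defects bleed at q (assumption). Closable defects then bleed at (8% − 0.2q)/0.8. Consider dropping non-closable patients from the clip arm only (0.8×460 = 368 against 460), tested at 0.05:

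| q | Clip-arm rate after dropping | Chance of a significant result |
|---|---|---|
| 8% | 8% | 5% |
| 12% | 7% | 8% |
| 16% | 6% | 20% |
| 20% | 5% | 40% |

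The plan does not propose this analysis. The table shows why a closable-only comparison needs the same record in both arms.

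**The case against.** The strongest reply is that the parallel time markers in Section 3.2.5 fit a staged allocation, with the clip factor drawn after resection. The design schematic (Figure 1) is not available here and may settle it. This stands: a reader might infer that endoscopists will resect knowing the clip arm, but the documents establish only that they can.

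A reader might also infer that closability is judged only once the arm is known. No section says when it is judged, so that is inference.

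A third tempting reading is that no unbiased comparison in closable defects is possible. Section 3.2.9.3 goes against it: an image after complete resection is mandatory in every case and available videos are collected, so closability could be rated centrally without knowledge of the arm. What is missing is a prespecified rating, not the raw material.

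Technique is also partly constrained and recorded. Cautery is randomised, the resection steps are common to both arms, visible residual tissue is to be treated in either arm, and resection pieces, adjunct measures, snare and polypectomy time are collected (Sections 3.2.6 and 3.2.9.3). Imbalance could therefore be described, though a description does not remove its effect.

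Finally, the intention-to-treat test is diluted, not biased, by non-closable defects, and the shift assumed in the power figures has no support in the documents. Both points are correct. Neither answers the lack of any instruction to withhold the clip arm during resection.

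**Conclusion.** The point holds as an ambiguity with a plausible route to performance bias. Sections 3.2.3 and 3.2.5 permit release of the clip arm before resection, one phrase in Section 3.2.5 may intend otherwise, and no available text withholds it. In an unblinded trial, sites could follow either reading.

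A reader might conclude that the primary comparison is confounded. The documents do not support that: the direction and size of any effect on technique are unknown. The losses of about 13 to 22 points of power rest wholly on an assumed one-point fall in no-clip bleeding, with 460 per arm and clip rates of 3% or 4%.

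On closability, the primary test is not biased. The gap is that the plan sets no arm-blind way to identify closable defects in the no-clip arm. The ambiguity should be removed because the protection is cheap and the analysis cannot supply it afterwards.

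**What to change.** State the same two-step release in Sections 3.2.3 and 3.2.5, from the same computer-generated list:

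1. Release the cautery setting after the decision to resect and before resection.
2. Release the clip arm only after all of the patient's study polyps have been declared resected and the endoscopist has recorded, for each defect, whether it looks closable (yes/no).

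In Section 3.2.10.1, keep the all-randomised comparison as primary. Prespecify a supportive clip versus no-clip comparison among patients whose defects were recorded as closable before the release, with the rule for patients with several study polyps set in advance. An arm-blind central rating of the post-resection images could serve as a check on the endoscopist's record.

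Cost: a second release step in the randomisation tool, one case report form field and a short pause before closure. The investigators should confirm that resecting all study polyps before any release is workable. Treatments, sample size and primary analysis stay as they are. Conduct after the release remains unblinded, so later actions on an open defect are not protected.
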